### **Amendment 1 (27 Jan 2022)**

This amendment is considered to be substantial based on the criteria set forth in Article 10(a) of Directive 2001/20/EC of the European Parliament and the Council of the European Union and any applicable local regulations.

### **Overall Rationale for the Amendment**

This protocol has been amended in response to queries raised by the UK MHRA regarding the inclusion of Japanese participants, wording on stopping rules, and the definition of abnormal laboratory findings.

In addition, a correction was made to the time that participants are required to be in the supine position prior to ECG timepoints, to align within the protocol.

Changes to the protocol are detailed below.

Section	Description of Change	Brief Rationale and/or Clarification
2.1 Study	Rationale included for the inclusion of	To clarify that Japanese participants have
Rationale	Japanese participants in the study.	been included in the study to meet
4.1 Overall Design		regulatory requirements of the ICH
		Guidance E5(R1), which provides a general
		framework for evaluating the potential
		impact of ethnic factors on the acceptability
		of foreign clinical data, with the underlying
		objective of minimizing duplication of
		clinical data, and it also describes the
		requirement of bridging studies for
		extrapolation of foreign clinical data to a
		new region.
7.1	Removal of "Individual Stopping Rules"	To clarify that as this is a single dose study,
Discontinuation of	from the section title, which previously read	individual stopping rules do not apply.
Study Intervention	"Discontinuation of Study	
	Intervention/Individual Stopping Rules".	
	The following text has also been removed	
	from the section:	
	As each participant will receive 1 SC or IV	
	dose in this study, discontinuation of study	
	intervention/individual stopping rules apply	
	only to participants who receive the IV dose.	
8.2.3	The time that participants should be in the	To align with footnote m of Table 2,
Electrocardiograms	supine position before each ECG timepoint	Schedule of Activities, which states 10
	has been changed from 15 to 10 minutes.	minutes before the ECG time point
8.2.4 Clinical	Removal of text stating that clinically	Removed because the study is conducted in
Safety Laboratory	significant abnormal laboratory findings are	healthy participants, not participants with a
Assessments	those which are not associated with the	disease. All abnormal laboratory results
	underlying disease, unless judged by the	will be considered clinically significant.
	Investigator to be more severe than expected	
	for the participant's condition.	

4.13.	1 Adverse Events	28	
4.13.	2 Deaths, Serious Adverse Events, and Other Significant Adverse Events	29	
4.13.	3 Clinical Laboratory Evaluation	29	
4.13.4	4 Vital Signs	30	
4.13.	5 ECG 30		
4.13.	6 12-Lead Holter ECG	31	
4.13.			
4.13.	8 Daylight Saving Time (DST):	32	
4.13.			
4.14	Immunogenicity Analysis		
	Biomarkers		
	Handling of Dropouts or Missing Data		
4.17	Subgroup Analysis		
4.18	Planned Interim Analyses		
	Changes in the Conduct of the Study or Planned Analysis		
5	REFERENCES		32
6	APPENDICES		33
6.1	Schedule of Assessments	33	
6.2	Imputation Rules for Partial Dates	40	
6.3	Laboratory Test Parameters		
6.4	ECG Notable Criteria		
6.5	Sample SAS Code for statistical analysis		

List of Tables

Table 1 Planned ALXN1910-HV-101 Dosing Cohorts	12
Table 2 Serum Pharmacokinetic Parameters After Single Dose Administration	14
Table 3 Pharmacokinetic Parameter and Estimation	22
Table 4 TEMA/PCS Criteria for Vital Signs	30
Table 5 Schedule of Assessments	
Table 6 Algorithm for Treatment-Emergent Adverse Events:	40
Table 7 Algorithm for Prior/Concomitant Medications Categorization:	

Alexion Pharmaceuticals, Inc.

ALXN1910-HV-101

Statistical Analysis Plan

REVISION HISTORY

Version No.	Effective Date	Summary of Change(s)
Final 1.0	07 Jun 2022	
Final 2.0	27 Jan 2023	Page 14, updated the sentence "nominal infusion time is within 5 seconds"
		Due to protocol amendment 3, and the major changes are the EOS visit for all participant is at Day 75, and ADA titer category analysis removed.
Final 3.0	27 Mar 2023	In Section 4.8.1, "Exposure to IMP data will be summarized using descriptive statistics for each treatment cohort" removed

Statistical Analysis Plan

LIST OF ABBREVIATIONS

Abbreviation/Acronym	Definition/Expansion		
ADA	Antidrug antibody		
ADAAS	Antidrug antibody analysis set		
AE	Adverse event		
AESI	Adverse events of special interest		
ANOVA	Analysis of variance		
ATC	Anatomical Therapeutic Chemical		
AUC	Area under the curve		
AUC∞	AUC from time zero extrapolated to infinity		
AUC _{0-t}	AUC from time zero to the last quantifiable concentration		
BA	Bioavailability		
BDRM	Blinded data review meeting		
BL	Biostatistician Lead		
BLQ	Below the lower limit of quantification		
BMI	Body mass index		
BP	Blood pressure		
bpm	Beats per minute		
CI	Confidence interval		
CL	Clearance		
CL/F	Apparent clearance following extravascular (non-intravenous) administration, e.g., clearance following oral, subcutaneous, topical, nasal, sublingual routes		
C _{max}	Maximum observed concentration		
C _{min}	Minimum observed concentration at steady state		
CPMS	Clinical Pharmacology, Modeling, and Simulation		
eCRF	Electronic Case Report Form		
CS	Clinically significant		
CSP	Clinical Study Protocol		
CS	Clinically significant		
CTCAE	Common Terminology Criteria for Adverse Events		

CONFIDENTIAL

Alexion Pharmaceuticals, Inc.

ALXN1910-HV-101

Statistical Analysis Plan

Abbreviation/Acronym	Definition/Expansion	
CV	Coefficient of variation	
СҮР	Cytochrome P450	
DBP	Diastolic blood pressure	
DRM	Data Review Meeting	
ECG	Electrocardiogram	
ENR	Enrolled Analysis Set	
EOS	End of study	
ET	Early termination	
Fe	Fraction of administered drug excreted unchanged in the urine	
Fe%	Urinary cumulative excretion as % of unchanged drug	
HBsAg	Hepatitis B surface antigen	
HCV	Hepatitis C virus	
HIV	Human immunodeficiency virus	
HR	Heart rate	
GMR	Geometric mean ratio	
IB	Investigator's Brochure	
ICF	Informed consent form	
IMP	Investigational medicinal product	
IV	Intravenous(ly)	
L	Linearity index	
LLOQ	Lower limit of quantification	
LOQ	Limit of quantification	
MAD	Multiple ascending dose	
MedDRA	Medical Dictionary for Regulatory Activities	
mRNA	Messenger ribonucleic acid	
MRT	Mean residence time	
MTD	Maximum tolerated dose	
NA	Not available	
NCS	Not clinically significant	

Statistical Analysis Plan

Abbreviation/Acronym	Definition/Expansion	
NK	Not known	
NR	Not reportable	
NS	No sample	
OTC	Over the counter	
PCS	Potentially clinically significant	
PD	Pharmacodynamic(s)	
PDAS	Pharmacodynamic analysis set	
РК	Pharmacokinetic(s)	
PKAS	Pharmacokinetic analysis set	
PTF	Peak trough fluctuation	
PTT	Peak-to-trough ratio	
QTc	corrected QT interval	
QTcF	QT corrected using Fridericia's formula	
RAS	Randomized Analysis Set	
SAD	Single ascending dose	
SAE	Serious adverse event	
SAF	Safety Analysis Set	
SAP	Statistical Analysis Plan	
SBP	Systolic blood pressure	
sc	Subcutaneous	
SD	Standard deviation	
SE	Standard error of the mean	
SI	Standard international	
SOC	System Organ Class	
t _{1/2}	Apparent terminal elimination half-life	
TEAE	Treatment-emergent adverse event	
TEMA	Treatment-emergent markedly abnormal	
t _{last}	Time to last quantifiable concentration	
t _{max}	Time corresponding to occurrence of C _{max}	

ALXN1910-HV-101	Statistical Analysis Plan

Abbreviation/Acronym	Definition/Expansion
Vz	Volume of distribution during terminal phase following intravenous dosing
V _z /F	Apparent volume of distribution during terminal phase following extravascular dosing
WHO-DD	World Health Organization - Drug Dictionary
λz	Terminal elimination rate constant

Statistical Analysis Plan

1 INTRODUCTION

This Statistical Analysis Plan (SAP) describes all planned analyses for the Clinical Study Report (CSR) of Study ALXN1910-HV-101, A Phase 1, Randomized, Double-blind, Placebo-controlled, Single Ascending Dose Study of Subcutaneously and Intravenously Administered ALXN1910 in Healthy Adult Participants. It describes the data to be analysed, including details of the statistical analyses to be performed.

The content of this SAP is based on the following study documents:

- Study ALXN1910-HV-101 protocol Amendment 3 dated 27 Jul 2022.
- Electronic Case Report Form (eCRF) Version 11. 06 May 2022.
- Data Management Plan (DMP) Final 1.0 dated 18 Mar 2022.

This SAP will be finalized prior to database lock. Should circumstances arise during the study rendering these analyses inappropriate, or if improved methods of analysis arise, updates to the analyses may be made. Any changes after the finalization of this SAP will be documented in Statistical Method Modification Form. Any deviations from the final SAP after database lock and all alternative or additional statistical analyses that may be performed will be discussed in the Clinical Study Report (CSR)(changes to planned analysis) and, if applicable, in an SAP addendum.

2 STUDY OBJECTIVES

The primary and secondary objectives of the study are as mentioned below:

2.1 Primary Objective

Objective	Endpoint
• To assess the safety and tolerability of ALXN1910	• Incidence of TEAEs and TESAEs

2.2 Secondary Objective

Objective	Endpoint
 To assess the PK of single ascending	• Serum ALXN1910 PK (activity) and
doses of ALXN1910	PK parameters
• To explore the PD effects of single ascending doses of ALXN1910	• Plasma concentrations of PPi, PLP, PL, and PA versus time profiles
 To assess the immunogenicity of	• Incidence and titers of treatment-
ALXN1910	emergent ADAs
 To assess the absolute bioavailability of ALXN1910 SC 	• GMR of AUC values of SC versus IV from serum concentrations of ALXN1910
• To compare the safety, tolerability, PK,	• Quantitative assessment of
and PD of ALXN1910 SC between	safety/tolerability and PK/PD
Japanese and non-Japanese healthy	parameters between Japanese and non-
participants	Japanese participants

Abbreviations: ADA = antidrug antibody; AUC = area under the serum concentration-time curve; GMR = geometric mean ratio; IV = intravenous; PA = pyridoxic acid; PD = pharmacodynamics(s); PK = pharmacokinetic(s); PL = pyridoxal; PLP = pyridoxal-5' -phosphate; PPi = inorganic pyrophosphate; SC = subcutaneous; TEAE = treatment emergent adverse event; TESAE = treatment emergent serious adverse event

Statistical Analysis Plan

2.3 Exploratory Objective(s)

Not Applicable.

3 INVESTIGATIONAL PLAN

3.1 Overall Study Design and Plan

This is a Phase 1, randomized, double-blind, placebo-controlled study designed to evaluate the safety, tolerability, PK, PD, and immunogenicity of SADs of ALXN1910 SC and a SAD of ALXN1910 IV in up to approximately 48 healthy adult participants across treatment cohorts (up to approximately 36 participants to receive ALXN1910 and up to approximately 12 participants to receive placebo) (Table 1). Of the 48 participants, 8 will be of Japanese descent, defined as those participants whose parents and grandparents are both Japanese and who have spent less than 10 years outside of Japan.

Cohortª	Number of Participants (ALXN1910:Placebo)	Route of Administration	Dose	Number of Doses/Dose Interval
1	8 (3:1)	IV ^b	5 mg	Single dose
2	8 (3:1)	SC	15 mg	Single dose
3	8 (3:1)	IV ^b	15 mg	Single dose
4	8 (3:1) (Japanese participants)	SC	15 mg	Single dose
5	8 (3:1)	SC	45 mg	Single dose
6	8 (3:1)	SC	135 mg	Single dose

 Table 1
 Planned ALXN1910-HV-101 Dosing Cohorts

^a Cohort 3, Cohort 4, and Cohort 5 can be initiated in parallel after dose escalation decision following SRC review of Cohort 2 safety and PK data.

^b Slow IV infusions (rate of infusion = 6 mL/h) using a controllable infusion pump. The pharmacy manual will include details regarding infusion rate and duration.

Abbreviations: IV = intravenous; PK =pharmacokinetic; SC = subcutaneous; SRC = Safety Review Committee

[figure not shown]
For this FIH study, 8 participants will be randomly assigned in a 3:1 ratio to treatment and placebo in each of the 6 cohorts with escalating doses of 5 mg IV (Cohort 1), 15 mg SC (Cohort 2), 15 mg IV (Cohort 3) in parallel with 15 mg SC in Japanese participants (Cohort 4) and 45 mg SC (Cohort 5), followed by 135 mg SC (Cohort 6). The first 2 participants randomized to each cohort will be dosed as a sentinel pair, with 1 participant on active treatment and 1 participant on placebo. This dosing strategy is justified given the large exposure margins (approximately 15-fold at the highest planned single dose of 135 mg SC).

Participants who meet the qualifications for the study based on screening will be admitted to the CRU the day prior to dosing (Day -1) to undergo Check-in assessments per the applicable SoA (Section 6.1).

Final determination of eligibility will be determined based on Check-in and predose procedures, and eligible participants will be randomized to ALXN1910 or placebo on Day 1 prior to dosing. There will be extensive PK/PD sampling during the first 24 hours after dosing. Safety assessments will be performed per the SoA. The study schematic is presented in Figure 1.

Statistical Analysis Plan

Figure 1 Study Design Schematic

3.2 Determination of Sample Size

No formal testing of hypotheses has been planned for this study. Therefore, no formal sample size calculations were performed. Approximately 48 participants are considered to be adequate to support and analyze the initial characterization of safety, tolerability, PK, PD, and immunogenicity for ALXN1910. The following table provides the probability of observing AEs under various underlying event incidence.

Incidence of AE in the Population	Probability to Observe at least 1 AE Occurrence in 6 Participants from Each Cohort
10%	46.9%
15%	62.3%
20%	73.8%
25%	82.2%
30%	88.2%
35%	92.5%
40%	95.3%

3.3 Endpoints and Associated Variables

The following endpoints will be used to investigate single ascending doses of ALXN1910 in participants.

Statistical Analysis Plan

3.3.1 Safety Variables

- Physical examinations
- Vital signs (Oral body temperature, pulse rate, respiratory rate, and supine blood pressure [BP])
- 12-lead electrocardiogram (ECG): Heart rate, PR interval, QRS interval, QT interval, QTC interval and QT interval using Fridericia's correction [QTcF]
- Clinical laboratory tests (hematology, clinical chemistry, coagulation, and urinalysis parameters)
- Treatment Emergent Adverse Event (TEAE) assessments
- Concomitant medication assessments

3.3.2 Pharmacokinetic Variables

Pharmacokinetic concentration data will be obtained at time point(s) described in the protocol, as detailed in Table 2 and Table 3 of study protocol and as follows:

Serum PK samples will be collected at the following nominal times: 0 (pre-dose sample), 30 min and, 2, 4, 8, 12, 24, 48, 72, 96 hours and on D6, D7, D8, D15, D22, D29, D36, D43 and D75 (after injection (for sc administration) or after start of infusion (for IV administration). The IV dose cohorts will also have an end-of-infusion PK time point (nominal infusion time is within 5 seconds and 0.5 hours for Cohort 1 and Cohort 3, respectively).

Unless otherwise stated, derivation of PK parameters will be the responsibility of Clinical Pharmacology, Modeling and Simulation (CPMS) group, Parexel.

If calculable, the following PK parameters listed in Table 2 will be determined for ALXN1910 in Serum following single SC or IV dose administration.

Parameter	WNL Name	CDISC Name	Definition
C _{max}	Cmax	CMAX	Maximum observed concentration
DNC _{max}	Cmax_D	CMAXD	Dose-normalized C _{max}
t _{max}	Tmax	TMAX	Time corresponding to occurrence of C_{max}
t _{1/2}	HL_Lambda_z	LAMZHL	Apparent terminal elimination half-life
λ_z	Lambda_z	LAMZ	Terminal elimination rate constant
AUCt	AUClast	AUCLST	AUC from time zero to the last quantifiable concentration
DNAUCt	AUClast_D	AUCLSTD	Dose-normalized AUCt
AUC ₀₋₁₆₈	AUC ₀₋₁₆₈	AUCINT	AUC from time zero to time 168 h

 Table 2 Serum Pharmacokinetic Parameters After Single Dose Administration

ALXN1910-HV-101

Statistical Analysis Plan

Parameter	WNL Name	CDISC Name	Definition
AUC∞	AUCINF_obs	AUCIFO	AUC from time zero extrapolated to infinity
$DNAUC_{\infty}$	AUCINF_D_obs	AUCIFOD	Dose-normalized AUC_{∞}
%AUC _{ex}	AUC_%Extrap_obs	AUCPEO	Percentage of AUC_{∞} obtained by extrapolation beyond t_{last}
CL or CL/F	Cl_F_obs	CLFO	Total body clearance (IV route)or apparent clearance (SC route)
V _d or V _d /F	Vd_F_obs	VZFO	Volume of distribution (IV route) or apparent volume of distribution (SC route)

Source: NCI EVS Terminology Resources website:

http://www.cancer.gov/cancertopics/cancerlibrary/terminologyresources/cdisc.

Additional PK parameters may be calculated if deemed appropriate.

3.3.3 Pharmacodynamic Variables

To assess the effect of ALXN1910 on pharmacodynamic (PD) variables PPi, PLP, PL, and PA versus time profiles, whole blood samples will be collected at the times specified in the Schedule of Assessments.

3.3.4 Immunogenicity Variables

ADA positive: Include participant with a positive response in the ADA assay at any time point will be categorized as follows:

- Pre-existing Immunoreactivity: Defined as ADA positive result in the assay at baseline with all post first dose ADA results negative or a positive result at baseline with all post first dose ADA results less than 4 folds over the baseline titer levels.
- Treatment-emergent ADA Responses: Defined as a positive result in the ADA assay post first dose, when baseline results are negative or missing.
- Treatment-boosted ADA responses: Defined as a positive result in the ADA assay post first dose, that is greater than or equal to 4-fold over baseline titer levels, when baseline results are positive.

ADA negative: ADA negative response in the ADA assay at all time points.

3.3.5 Exploratory Variables

Biomarker assays may be conducted as exploratory analyses on collected whole blood samples.

4 STATISTICAL METHODS

4.1 Data Quality Assurance

All tables, figures, and data listings to be included in the report will be independently checked for consistency, integrity, and in accordance with standard Parexel procedures.

4.2 General Presentation Considerations

This section is not applicable to PK data.

4.2.1 Treatment

During this study up to approximately 48 participants will be randomized in a 3:1 ratio to receive either of ALXN1910 or placebo as mentioned in Table 1.

4.2.2 Study Day

Study days will be numbered relative to the first day of study drug administration.

• If the date of event is before the study drug administration, then:

Study day = (Date of measurement – Date of study drug administration [i.e. Day 1] in each cohort)

• If the date of event is on or after the study drug administration, then:

```
Study day = (Date of measurement – Date of study drug administration [i.e. Day 1] in each cohort) + 1
```

4.2.3 End of Study

The end of the study is defined as the date the last participant completes the last safety follow up.

End of study visit is planned on Day 75.

A participant is considered to have completed the study if they complete all visits of the study including the last scheduled visit specified in the SoA.

4.2.4 Baseline

Baseline is defined as the last non-missing measurement recorded before first dose of study drug administration.

Measurements taken in triplicates:

For safety parameters (e.g. ECGs), where the study requires multiple replicates (e.g. triplicates) per time point, the average of these measurements would be calculated (if not already available in the database) before determining baseline.

Baseline is defined as average of non-missing triplicate measurement collected prior to study drug administration.

No imputation will be done for missing baseline value for derivation of change from baseline or summary tables and shift tables.

Statistical Analysis Plan

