- m Each ECG timepoint during the study will be 12-lead and performed in triplicate sequentially within 5 minutes, at least 1 minute apart after 10 minutes of bedrest in supine position (note, no bedrest is required post ECG), at Screening and 90, 75, and 60 minutes before dosing. ECGs should not be performed within 1 hour after any major meal or major meals should be withheld until after ECG assessments.
- n Investigators should review Day 5 laboratory results to ensure each participant is suitable for discharge.
- ° The IV dose cohorts will also have an end-of-infusion PK time point.
- p Spot urine collection.
- q Sample for ADA assessments will be collected prior to administration of the drug. In the event of suspected SAE like hypersensitivity or anaphylaxis, additional samples may be collected for ADA assessments at or near the event.
- r See Section 10.4 for details.
- s Collect 3 lab samples after a suspected hypersensitivity reaction: as soon as possible and at 2 and 8 hours after the suspected reaction (+ 1 hour window for each sample). If the suspected hypersensitivity reaction persists beyond 8 hours, the CRU should contact the Medical Monitor for guidance. Predose samples will only be analyzed for participants with a reported suspected hypersensitivity reaction.

Abbreviations: ADA = antidrug antibody; BMI = body mass index; C5b-9 = terminal complement complex; CRU = clinical research unit;

ECG = electrocardiogram; h = hours; HIV = human immune deficiency virus; I = injection; ICF = informed consent form; IEC = Independent Ethics Committee;

OP = outpatient; min = minutes; PA = pyridoxic acid; PD = pharmacodynamic; PK = pharmacokinetic; PL = pyridoxal; PLP = pyridoxal 5'-phosphate;

PPi = inorganic pyrophosphate; SOI = start of infusion; TEAE = treatment-emergent adverse event; TESAE = treatment-emergent serious adverse event

Table 3: Schedule of Activities – Single Ascending Dose Cohorts (Day 6 through Day 75)

Study Day a	Day 6 post	Day 7 post	Day 8 post	Day 15 post	Day 22 post	Day 29 post	Day 36 post	Day 43 post	Day 75 post I/SOI		
Status (OP or CRU)	I/SOI	I/SOI	I/SOI	I/SOI	I/SOI O	I/SOI P	I/SOI	I/SOI	(EOS/ED b )		
Full physical examination								X			
Brief physical examination			X	X		X					
Vital sign measurements c			X	X		X		X			
12-lead ECG (triplicate) d	X	X	X	X				X			
Chemistry			X	X	X	X	X	X	X		
Hematology			X	X	X	X	X	X	X		

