## 8.2.3. Electrocardiograms

- At each timepoint indicated in the SoA (Section 1.3), 12-lead ECGs will be performed in triplicate sequentially within 5 minutes, at least 1 minute apart to obtain heart rate, PR, QRS, QT, and QTc intervals.
- ECGs should not be performed within 1 hour after any major meal or major meals should be withheld until after ECG assessments.
- Participants should rest in supine position for at least 10 minutes before each ECG timepoint.
- Predose ECGs (Baseline) should be performed at least 1 minute apart after 10 minutes of bedrest in supine position (note, no bedrest is required post ECG), at 90, 75, and 60 minutes before dosing.
- Postdose ECGs will be performed before the coinciding blood collection, whenever possible.

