4.13.5 ECG

Standard safety 12-lead ECGs will be performed as shown in the Section 6.1.

The following ECG parameters will be recorded:

Heart rate (HR) (beats per minute [bpm]) PR interval (msec) QRS interval (msec) QT interval (msec) QTc interval (msec)

QTcF interval (msec)

The ECG will be evaluated by the Investigator as 'Normal', 'Abnormal, NCS' or 'Abnormal, CS'.

All ECG parameters will be listed by participant including changes from baseline by dose cohort, including pooled placebo, pooled active treatment across cohorts, pooled IV cohorts, pooled SC cohorts and overall.

Baseline is defined in Section 4.2.4.

Descriptive statistics for absolute values and changes from baseline will be presented by cohort. A categorical QTc analysis will also be performed.

Measurements obtained at Screening will not be included in the shift tables.

A summary of the number and percentage of participants with the following QT/QTc intervals of ECG parameters will be displayed in a frequency table at each visit by dose cohort, including pooled placebo, pooled active treatment across cohorts, pooled IV cohorts, pooled SC cohorts and overall cohort:

ALXN1910-HV-101

Statistical Analysis Plan

- QT, QTcF interval ≤ 450 msec
- 450 msec < QT, QTcF interval \leq 480 msec
- 480 msec < QT, QTcF interval \leq 500 msec
- QT, QTcF interval > 500 msec
- QT, QTcF interval increases from baseline ≤ 30 msec
- 30 msec < QT, QTcF interval increases from baseline ≤ 60 msec
- QT, QTcF interval increases from baseline > 60 msec

The listing of ECG abnormality will be presented separately.

Mean of the triplicates for ECG measurements will also be presented in the listing and used for deriving baseline and change from baseline.

4.13.6 12-Lead Holter ECG

Not applicable.

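### SAP 4.2.4 does not say how the three predose ECG time points form the baseline, and its most natural reading uses only the last of them

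*SAP*

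**What the plan says.** Protocol 8.2.3 ties the word baseline to the predose recordings: "Predose ECGs (Baseline) should be performed at least 1 minute apart after 10 minutes of bedrest in supine position", with the times given as "at 90, 75, and 60 minutes before dosing". Footnote m to Table 2 of the protocol's Schedule of Activities sets the replication: "Each ECG timepoint during the study will be 12-lead and performed in triplicate sequentially within 5 minutes". The same footnote also schedules an ECG at Screening: "at Screening and 90, 75, and 60 minutes before dosing".

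SAP 4.2.4 opens with a rule for all variables: "Baseline is defined as the last non-missing measurement recorded before first dose of study drug administration". Under a sub-heading for triplicate measurements, it says of the replicates at a time point that "the average of these measurements would be calculated (if not already available in the database) before determining baseline". A further sentence follows: "Baseline is defined as average of non-missing triplicate measurement collected prior to study drug administration".

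SAP 4.13.5 refers back to 4.2.4 and adds: "Mean of the triplicates for ECG measurements will also be presented in the listing and used for deriving baseline and change from baseline". It keeps Screening out of the shift tables but does not mention Screening in connection with baseline. Protocol 9.4.1 averages the readings within a triplicate and gives no rule for combining the three predose time points.

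**The concern.** The protocol collects three predose triplicates and calls them baseline, but the analysis plan never names the three times. A programmer who averages each triplicate and then takes the last value before dosing uses the one at 60 minutes and leaves the other two unused. Another programmer could average everything recorded before dosing, because the triplicate sentence sets no limit on which recordings count.

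Baseline enters every ECG change from baseline and the change categories with cut-points at 30 and 60 msec (protocol 9.4.1; SAP 4.13.5 and 6.4). It would also enter the concentration-QTc analysis that protocol 9.4.1 allows. Noise in a participant's baseline carries into all of that participant's postdose changes. Each active cohort has six participants, so one participant changing category moves a cohort percentage by 1/6 = 16.7 points.

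**Working it through.** The plan states no figure for the ECG baseline and no QTcF variance, so there is nothing to reproduce. All SDs and correlations below are assumptions.

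**Readings available.** Triplicates are taken within 5 minutes, and the predose times are 15 minutes apart. The three times therefore cannot be one triplicate. There are 3 × 3 = 9 predose readings on Day 1, plus a Screening triplicate. Taking the last triplicate mean uses 3 of the 9.

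**Notation.** b is the SD between recording occasions within a day, w the SD of a single reading, and ρ the correlation between the occasion effects at the three predose times. The postdose occasion is one triplicate, taken as independent of the predose occasions.

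- Variance of one triplicate mean: b² + w²/3
- Variance of the mean of three triplicate means: b²(1 + 2ρ)/3 + w²/9
- SD of change: square root of (postdose variance + baseline variance)

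**Main case, b = w = 6 msec.** One triplicate has variance 36 + 12 = 48. With the last triplicate as baseline, the SD of change is √(48 + 48) = 9.80 msec. With all three triplicates:

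| ρ | Baseline variance | SD of change (msec) | Reduction from 9.80 |
|---|---|---|---|
| 0 | 12 + 4 = 16 | √64 = 8.00 | 18% |
| 0.5 | 24 + 4 = 28 | √76 = 8.72 | 11% |
| 0.75 | 30 + 4 = 34 | √82 = 9.06 | 7.6% |
| 1 | 36 + 4 = 40 | √88 = 9.38 | 4.3% |

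**Other SDs.**
- b = 8, w = 6: 12.33 msec against 10.07 (ρ = 0), 11.08 (ρ = 0.5) and √(76 + 68) = 12.00 (ρ = 1). The last is a reduction of 2.7%, so 4% is not a floor for every choice of SDs.
- b = 5, w = 8: 9.63 msec against 7.86 (ρ = 0) and 8.37 (ρ = 0.5).

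**Later visits.** A day-to-day SD s adds 2s² to the variance under both baselines. Take b = 5, w = 8 and ρ = 0, so that one triplicate mean has variance v = 25 + 64/3 = 46.33. With s = 10 msec, the SD is √(200 + 92.67) = 17.11 for the last triplicate and √(200 + 61.78) = 16.18 for all three. The reduction is 5.4%, against 18% on Day 1 with the same b, w and ρ.

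**Chance crossings of 30 msec.** In the noisiest case tried (occasion SD 7, single-reading SD 10, ρ = 0), the Day 1 SD of change is 12.83 msec with the last triplicate and 10.48 msec with all three. Under a normal distribution with no drug effect, the chance of an increase above 30 msec at one Day 1 time point is 0.97% and 0.21% respectively.

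**If Screening were averaged in.** With four triplicates and ρ = 0, the variance of Day 1 change is 1.25v + s²/8, against 4v/3 without Screening. It is larger only when s² exceeds about 0.67v. At later visits it is 1.625s² + 1.25v against 2s² + 4v/3, which is always smaller. The risk from Screening is therefore mainly bias: a Screening offset of 2 to 10 msec moves a four-triplicate baseline by 0.5 to 2.5 msec.

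**The case against.** A reader might infer that the SAP holds two contradictory ECG baselines. The text does not require this. The opening sentence covers all variables, the other sits under its own sub-heading, and the two can be read together as averaging each triplicate and then taking the last. Nor does the SAP contradict a protocol formula, because the protocol labels the predose ECGs as baseline without saying how to combine them. The SAP leaves the combination undefined.

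A reader might also infer that Screening is part of baseline. No text says so. It is only not excluded, and as the working shows it would not in general add noise.

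SAP 4.2.5 averages several planned assessments at one time point, and Predose is a single column in the schedule. That gives some support for averaging the three triplicates without Screening. But 4.2.5 governs summary statistics and figures, and the three predose recordings have separate stated times, so it does not settle the baseline.

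Exclusion criterion 5 speaks of a triplicate ECG predose on Day 1. If the recordings at 90, 75 and 60 minutes were themselves that single triplicate, the SAP's triplicate sentence would already give their mean. Footnote m points the other way, since each time point is a triplicate completed within 5 minutes.

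The objection on size stands. Recordings 15 minutes apart may be highly correlated, which puts the gain towards the low end, and day-to-day variation dilutes it at later visits.

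**Conclusion.** The point holds as a gap with a modest cost in precision. SAP 4.2.4 does not define how the three predose time points form the ECG baseline, and its most natural reading uses one of the three. With b = w = 6 msec, averaging all three would make the SD of Day 1 change about 4% (ρ = 1) to 18% (ρ = 0) smaller, with less gain at later visits. These figures rest on assumed variances and on independence of the postdose occasion from the predose occasions.

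The reach is limited to ECG change summaries, the 30 and 60 msec categories and any concentration-QTc analysis. The primary endpoint is the incidence of TEAEs and TESAEs, no hypotheses are tested, and the QT stopping rule in protocol Table 11 uses the absolute uncorrected QT interval, so none of these depends on the ECG baseline. This is an improvement available at no cost in data and does not threaten the trial's main conclusions.

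**What to change.** Keep the general last-non-missing rule in SAP 4.2.4, because laboratory and vital-sign changes depend on it. Replace only the closing definition under the triplicate sub-heading with:

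*ECG baseline is the mean of the available triplicate means from the scheduled Day 1 predose ECGs at 90, 75 and 60 minutes before dosing; Screening ECGs are not used.*

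Also state how repeat predose triplicates are handled. Exclusion criterion 5 allows up to two additional triplicates, and SAP 4.2.5 lets a repeat assessment qualify as baseline. Apply the same baseline in SAP 4.13.5 and 6.4.

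The cost is a sentence or two of SAP text and the matching derivation; the readings are already scheduled. The change should be recorded before database lock, through the modification form that SAP section 1 provides for, so that the choice is not made with results in view.
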